5.2.9. Staff Questionnaires - group A

At the end of the study, staff will be required to complete a usability questionnaire assessing the convenience of using the system and the user interface. Two different questionnaires will be used for either physician users and nurse users participating in the study. The questionnaires will include a variety of questions such as YES/NO, open-ended and scoring-based questions.

5.3. Group B- Control Group

5.3.1. Nutrition camera - group B

Local site procedure for changing feeding bottle/bag should be followed as needed and according to hospital procedures. An additional camera (Nutrition camera) will be added, pointed directly at the feeding bottle/bag area and not on the patient.

The Nutrition camera will record a real time video and automatically save it in storage device (such as PC). This camera captures the amount of feeding discarded that was not used for patient feeding. It will allow later data analyzation to quantify the amount of feeding discarded by using the grid lines marked on the feeding bag's/bottle's exterior. In order to ensure the effectiveness of the Nutrition camera, it will bear an instruction such as Ensure camera points at feeding bottle/bag.

5.3.2. REE or calorimeter measurement- group B

Once the patient is enrolled in the study a baseline REE or calorimeter measurement (according to gold standard in the department) should be taken using available department equipment.

5.3.3. Feeding program - group B

Once the REE \ calorimeter measurement \ other method to determined caloric target is obtained, personnel authorized by the hospital should administer a suitable feeding program per hospital standard of care (i.e., hospital's usual available feeding tubes, feeding pumps, gravity feeding, etc.).

5.3.4. On-going treatment- group B

Subject: smART Plus Comparative Study Protocol - Beilinson

Patients in the control group should be treated in accordance with standard hospital procedures per usual hospital/physician determined treatment plan.

[figure not shown]
5.3.5. Data recording- group B

The following information will be acquired from the patient's medical chart (recorded in the hospital sources) for each patient:

- Initial screening: as detailed in the study eCRF
- Feeding information: Food types, amounts, rate, water delivery, parenteral nutrition, TPN, Indirect calorimeter and other nutritional data.
- Gastric residual volume: discard gastric residuals amount, GRV procedure times.
- Medications provided: as detailed in the study eCRF.
- Lab results: all patient lab results ordered during the study as well as all available lab results obtained 24 hours prior to study enrollment and added to the eCRF.
- Imaging: patient imaging (X-rays, CT, and alike) performed during the study should be obtained and added to the eCRF.
- Urine monitoring: amounts, rates, times, warnings and all data related to urinary output and diagnosis, and found in the hospital source.
- ICU submission and discharge ordering times
- Breathing data reports starting from the ICU admission (FiO2, PEEP)
- Demographics

5.4. Study Flowchart

Subject: smART Plus Comparative Study Protocol - Beilinson

5.5. Schedule of Activities (SoA)

Subject: smART Plus Comparative Study Protocol - Beilinson

Procedures	Screening/ enrollment	Medical Device Placement	Ongoing use	Termination
Day	1	1(T)	Up to 14	1 up to 14
Informed Consent	T+C			
Eligibility Criteria	T+C			
Physical Exam	T+C			
Pregnancy test (if applicable)	T+C			
Videotaping		T+C	T+C	
Vital Signs		T+C	T+C	T+C
REE or calorimeter/spirometer measurement		T+C	T as needed and according to procedures	
Lab Data			T+C	T*+C*
Medical Device Administration		T	T	
GRV Measurements			T+C as needed and according to procedures	
Urine monitoring			T as needed and according to procedures	
Adverse Events	T+C	T+C	T+C	T+C
Concomitant Medication		T+C	T+C	T+C
Information regarding nutritional supplement administration		T+C	T+C	

T – group A – "Treated"

C – group B – "Control"

* - For T only – obtained retroactively 24 hours prior the feeding tube insertion and during the ongoing study

6. Preparation/Handling/Storage/Accountability

6.1. Acquisition and accountability

All disposables and capital equipment will be provided to the investigator directly by the sponsor.

The site will store the capital equipment throughout the entire period of the trial.

The disposables will be delivered to the sites (in quantities or in individuals) according to the enrollment rate. The sponsor will ensure that the site has a sufficient amount of equipment (capital

 ART MEDICAL PATIENT SAFETY TECHNOLOGY	Number: CRO-C-2822	Date issued: 01-Mar-2021
	Rev.06	Page 24 of 35

Subject: smART Plus Comparative Study Protocol - Beilinson

and disposable) for replacement of damaged equipment/parallel experiments/additional participants.

Device Receipt logs will be updated accordingly.

6.2. Used/unused devices

Used disposable devices will be discarded after opening/ use according to hospital procedures. Accountability logs will be updated accordingly.

All unused devices and study materials will be collected by the sponsor as needed at the end of the study.

6.3. Packaging and labeling

smART+ System information can be obtained from the:

- Investigator brochure (IB)
- Package or device labeling/instruction for use (IFU)
- Device quick guides
- User manual

7. Study Discontinuation and Participant Discontinuation/Withdrawal

7.1. Participant Discontinuation/Withdrawal from The Study

Each subject (or delegate) will be informed of his/her right to withdraw from the study at any time and for any reason. The Investigator may withdraw a subject from the study at any time if he considers that remaining in the study compromises the subject's health.

Additional criteria for discontinuation/withdrawal:

- The insertion of the feeding tube has failed after 3 attempts in each nostril
- Disease progression which requires discontinuation of the study intervention
- If the participant meets an exclusion criterion (either newly developed or not previously recognized) that precludes further study participation.

In the event a subject discontinuation/withdraws from the study the following procedures will be observed:

- The reasons for any subject discontinuation/withdrawal will be recorded on the study completion form of the eCRF.
- The investigator will inform the sponsor of the subject's early withdrawal for any reason.
- If withdrawal is caused by an adverse event that the investigator considers may be related to the device, it will be reported to the IRB and to the Sponsor.

Subjects who signed the informed consent form and are randomized but do not receive the study intervention are considered screen failures and may be replaced. Subjects who sign the informed consent form, and are randomized and receive the study intervention, and subsequently withdraw, or are withdrawn or discontinued from the study may also be replaced.

 ART MEDICAL PATIENT SAFETY TECHNOLOGY	Number: CRO-C-2822	Date issued: 01-Mar-2021
	Rev.06	Page 25 of 35

Subject: smART Plus Comparative Study Protocol - Beilinson

In addition, this study may be temporarily suspended or prematurely terminated if there is sufficient reasonable cause.

Circumstances that may warrant termination or suspension include according to the PI decision, but are not limited to:

- Determination of unexpected, significant, or unacceptable risk to participants
- Demonstration of efficacy that would warrant stopping
- Insufficient compliance to protocol requirements
- Data that are not sufficiently complete and/or evaluable
- Determination that the primary endpoint has been met
- Determination of futility

Study may resume once concerns about safety, protocol compliance, and data quality are addressed, and satisfy the sponsor, IRB and/or Food and Drug Administration (FDA).

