7.3. Follow-Up

No follow-up will be conducted for this study. AE and SAE collection is to be conducted up until the moment the subject study participation is terminated. AEs and SAEs occurring after study termination are not to be collected or reported for the purpose of this study.

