9.1 Sample size consideration

Approximately 200 subjects will be enrolled for the complete multi-center comparative study (100 per group). An interim analysis will be performed after 100 subjects (50 in each group) are enrolled on the primary endpoint.

1- Based on the primary endpoint at interim analysis (feeding efficiency):

Sample size rationale:

The rationale for sample size calculation is based on a difference in feeding efficiency between the tested group (with smART+ System) and the current standard practice (group B).

Sample size justification:

The comparison between groups of food consumption estimations is reflected by Effect size, calculated as the difference between the groups normalized by the common standard deviation.

The calculation uses the following formulation: (Estimation in the tested group - Estimation in control group)/Common standard deviation Error! Bookmark not defined.Error! Bookmark not defined.

A sample size of 50 in each group will have 90% power to detect an **effect size of 0.70** using a two-group t-test with a 0.025 two-sided significance level. [1, 2]

A significance of 0.025 was used instead of the usual 0.05 (alpha adjustment) due to the increase in the chance of making a Type 1 error following two subsequent analysis.

2- Based on the secondary endpoints at end of study:

2.1 Ventilation days:

Sample size rationale:

Subject: smART Plus Comparative Study Protocol - Beilinson

The rationale for sample size calculation is based on a difference in Ventilation days between the tested group (with smART+ System) and the current standard practice (group B).

Sample size justification:

The comparison between groups in ventilation days is reflected by Effect size.

A sample size of 100 in each group will have 90% power to detect an **effect size of 0.46** using a two group t-test with a 0.05 two-sided significance level. [1, 2]

2.2 Ventilation Associated Events:
Sample size rationale:

The rationale for sample size calculation is based on a difference in the proportion of subjects with Ventilation-Associated Events between the tested group (with smART+ System) and the current standard practice (group B) of 20%.

Sample size justification:

A two group continuity corrected c^2 test with a 0.05 two-sided significance level will have 90% power to detect the difference between a Group 1 proportion, p_1 , and a Group 2 proportion, p_2 (**odds ratio of 2.70**) when the sample size in each group is 100.[3]

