- The two-sample T-test or Non-parametric Wilcoxon-Mann-Whitney Rank sum test for independent samples (as is appropriate) will be applied for testing the statistical significance of the difference in the estimated nursing time that was expended for GRV activities, and the amounts of GRV removed from the patient between the study groups.
- Convenience of use of the system and the user interface scores (by subjective staff questionnaire) will be summarized in an appropriate table by study group
- The two-sample T-test or Non-parametric Wilcoxon-Mann-Whitney Rank sum test for independent samples (as is appropriate) will be applied for testing the statistical significance of the difference in the assessment of urine flow monitoring related to patient condition and usability between the study groups.
- The two-sample T-test or Non-parametric Wilcoxon-Mann-Whitney Rank sum test for independent samples (as is appropriate) will be applied for testing the statistical significance of the difference in ICU length of stay (measured from admission to ICU until the decision to discharge is ordered) between the study groups.
- Chi-square test or Fisher's Exact test (as is appropriate) will be applied for testing the statistical significance of the difference in percent of subjects experiencing Ventilation associated events between the study groups.

9.2.5 Safety:

Adverse events will be coded using the Medical Dictionary for Regulatory Activities (MedDRA, most updated version) terminology and presented in tables by System Organ Class (SOC) and Preferred Term (PT).

Subject: smART Plus Comparative Study Protocol - Beilinson

AE data will be listed individually and summarized by SOC and by PT within a system organ class for each study group.

Frequency of TEAEs (Treatment-Emergent Adverse Events) and device-related adverse events will be summarized in tables by SOC, PT and study group and by seriousness.

Chi-square test or Fisher's Exact test (as is appropriate) will be applied for testing the statistical significance of the difference in percent of subjects experienced any AE, drug-related AE and SAE between the study groups.

Concomitant medications entered into the database will be coded using the World Health Organization (WHO) Drug Reference List, which employs the Anatomical Therapeutic Chemical classification system.

10. Regulatory, Ethical, and Study Oversight Considerations

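### VAE is compared as a percent of subjects with no stated observation window, so time at risk and the patients counted can differ between the arms

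*Combined protocol and SAP*

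**What the plan says.** - **Endpoint and test.** Section 2.2 defines VAE only by reference to the latest CDC definition. Section 9.2.3 applies a chi-square or Fisher test to the "difference in percent of subjects experiencing Ventilation associated events between the study groups". There is no ventilator-day denominator, time-to-event method or rule for competing events, and no start or end of the VAE window.
- **End of participation.** A patient completes the study once enteral feeding is no longer needed (3.2). Comfort-oriented care also ends participation (7.2), and the synopsis caps it at 14 days. Section 7.3 states "No follow-up will be conducted for this study".
- **Withdrawal criteria.** Section 7.1 lists "The insertion of the feeding tube has failed after 3 attempts in each nostril" and "Disease progression which requires discontinuation of the study intervention". Neither names an arm.
- **Replacement.** Under 7.1, a randomized patient who never receives the intervention is reclassified as a screening failure and may be replaced. A treated patient who later leaves may be replaced too. Section 9.2 defines no analysis set.
- **Ventilator data.** Sections 5.2.8 and 5.3.5 list, for both arms, "Breathing data reports starting from the ICU admission" (FiO2 and PEEP). A start is given, but no end.
- **Sizing.** VAE is one of three secondary endpoints with its own sample-size statement in 9.1.

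**The concern.** A comparison of crude percentages is fair only if both arms are watched for VAE over comparable time and all randomized patients are counted. A patient is at risk of VAE for as long as ventilation lasts. The plan ties participation to feeding, the tube or the intervention instead, and it allows some randomized patients to be replaced.

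The device arm has more ways to meet these rules. Section 5.2.3 describes insertion of a study tube for group A only, section 5.3.3 has group B fed through the hospital's usual tubes, and the schedule in 5.5 gives device placement and administration to group A alone. If a worsening, still-ventilated group A patient leaves under 7.1 and a similar control patient stays, events are lost from one arm. Part of an apparent reduction in VAE could then come from the exit rules rather than the device.

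**Working it through.** **The plan's own figure.** Section 9.1 says that a "continuity corrected c^2 test with a 0.05 two-sided significance level will have 90% power" for an "odds ratio of 2.70" "when the sample size in each group is 100". The two proportions are left as symbols, and it is unclear whether the 20% mentioned there is the control rate or the difference. With one proportion at 20%, the odds are 0.25; 0.25 × 2.70 = 0.675, so the other is 0.675/1.675 = 40.3%. The continuity-corrected Fleiss formula then needs 115 per group, and power at 100 is 85.1%. A fall from 20% to 8.5% (the same odds ratio) needs 209. Starting from 30%, it needs 98. The stated figure is therefore not reproduced at 20%, though it is roughly met at some other base rates. That is a separate matter and nothing below depends on it.

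**Inputs for the bias check.** From the documents: a 14-day cap, 100 per group, two-sided 0.05. Assumed, because the documents give no values: 14-day VAE risk r = 20% or 30%; constant hazard; no device effect; a fraction f = 10% or 20% of group A leaving on day d = 4 or 7, kept in the denominator and otherwise ventilated to day 14; no such exits in group B; leavers' hazard h = 1 or 2 times average.

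**Formula.** Daily hazard λ = −ln(1 − r)/14, which is 0.01594 for r = 20% and 0.02548 for r = 30%. The loss in group A's observed proportion is f × [exp(−dhλ) − exp(−14hλ)].

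| | Smallest (r 20%, f 10%, d 7) | Largest (r 30%, f 20%, d 4) |
|---|---|---|
| h = 1 | 0.10 × (0.8944 − 0.8000) = 0.9 points | 0.20 × (0.9031 − 0.7000) = 4.1 points |
| h = 2 | 0.10 × (0.8000 − 0.6400) = 1.6 points | 0.20 × (0.8156 − 0.4900) = 6.5 points |

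**Effect on the test.** For h = 1, with group B at r and 100 per group, the normal approximation without continuity correction gives a two-sided false rejection rate of 5.3% to 9.8% instead of 5%.

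**Sensitivity to extubation.** If leavers would have had only 3 more ventilated days, replace 14 by d + 3 in the formula. The loss shrinks to 0.4-1.3 points (h = 1) or 0.7-2.3 points (h = 2).

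**Patterns that act differently.**
- *Removal and replacement.* Suppose 5-20% of group A is removed, with k times the VAE risk of the rest, and overall risk is 20%. The remaining risk is 0.20/(1 − f + fk): 20.5-22.2% for k = 0.5, 20.0% for k = 1, and 19.0-16.7% for k = 2.
- *Feeding ends earlier in group B.* If group B is watched for 10 days and group A for 14, group B shows 1 − exp(−10 × 0.01594) = 14.7% against 20%. The bias then runs against the device.

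**The case against.** A reader might infer that the two criteria in 7.1 apply only to group A, that group A is therefore watched for less time, and that its VAE rate is lowered. The documents do not support that as fact, for five reasons.

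- Neither criterion names an arm. Section 5 uses the term study intervention for procedures in both groups, and control patients also need a feeding tube. The device-arm reading is the natural one, given how 7.1 and 5.5 are worded, but it remains a reading.
- The stop in 7.3 is explicit for adverse-event collection. VAE rests on chart FiO2 and PEEP with no stated end, and ICU stay is measured to the discharge order, so chart data may be meant to run on. The ban on follow-up points the other way without settling it.
- Several exits can occur in either arm: withdrawal by the investigator for health reasons, a newly met exclusion criterion, comfort care and the end of feeding.
- A patient whose first insertion fails, and who so never receives the intervention, is reclassified and may be replaced. That is exclusion after randomization, not shortened observation, and the calculation for day 4-7 leavers does not describe it.
- The direction is open. Replacement can raise or lower group A's rate. If VAEs were picked up through adverse-event pages, the narrower recording for group B in 7.4.1 would lower group B's count instead.

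All five stand as limits on the conclusion. They do not remove the underlying gap: the endpoint is a crude percent, no rule fixes a common window, and no rule keeps every randomized patient in the count.

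**Conclusion.** The plan allows both the time at risk and the set of patients counted for VAE to differ by arm, because participation is not tied to ventilation, no VAE window is given, and randomized patients who exit may be replaced. If worsening, still-ventilated patients leave mainly from group A, its VAE percent is lowered with no true effect. The 0.9-4.1 and 1.6-6.5 point ranges show how large that could be, but they rest wholly on assumed exit rates, exit days, base risk and continued ventilation. They are not estimates for this trial, and neither the direction nor the size of any bias is established. The change should be made before VAE results are interpreted. It concerns a secondary endpoint and does not touch the primary comparison of feeding efficiency.

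**What to change.** Leave the clinical criteria for stopping the device or feeding as they are, and change only what happens to data collection and counting.

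1. In 3.2, 7.1, 7.2 and 7.3, separate stopping the device or feeding from withdrawal from data collection. The latter should occur only when consent is withdrawn.
2. In 9.2.3, count VAE for all randomized patients in their assigned arm, including failed insertions and anyone who is replaced.
3. State one window for both arms: from randomization to the earliest of end of ventilation, ICU discharge order, death or day 14, whatever the status of feeding, tube or device.
4. Derive VAE in that window from the FiO2 and PEEP chart data already listed in 5.2.8 and 5.3.5, and give that extraction the same end point in both arms.

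The cost is protocol wording plus extra chart extraction and data entry for patients who come off the device or feeding early. No new patient procedure is needed.

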4.5. Screen Failures

Screen failures are defined as participants who were examined by the PI/Co-investigator as part of the initial screening process and were not subsequently entered to the study (e.g., patient found to be ineligible by the PI/Co-investigator, informed consent was not obtained, PI/Co investigator's discretion, etc.).

A minimal set of screen failure information is required to ensure transparent reporting of screen failure participants, to meet the Consolidated Standards of Reporting Trials (CONSORT) publishing requirements and to respond to queries from regulatory authorities. Minimal information includes patient demographics, screen failure details, eligibility criteria, and any serious adverse event (SAE).

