4.6. Enrollment

Patients may be included in the study only if:

- The assessment performed as part of the initial screening (part of the eCRF) is acceptable and patient was found appropriate to participate in the trial, according to the PI (or co-investigator) decision.
- Informed consent has been obtained.
- For women of childbearing age, a negative urine (or blood) pregnancy test.

5. Study Intervention

Following the initial screening procedure and after patient was found to be eligible to participate in the study, patients shall be divided into two study groups:

Group A- ICU patients receiving the investigational device ("Treated")

Group B- Control group, receiving treatment according to local SOC.

The study intervention describes all study procedures and evaluations to be done as part of the study to support the determination of the primary and secondary objectives outlined in this protocol. Study source documents are defined as data collected from patient's medical chart (recorded in the hospital sources) as well as data collected by the smART+ System, as detailed in sections 5.2.8. and 5.3.5. below. In addition, video recording (as detailed in sections 5.2.1. and 5.3.1.) will be also used for later data analysis and serves as source data.

Subject: smART Plus Comparative Study Protocol - Beilinson

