5.1. Divisions into Groups

After completion of the “initial screening” chapter in the study eCRF recruitment cycle, and after patient was found likely to participate in the trial, patients will randomly be divided into two groups.

Measures to minimize bias: randomization and blinding

Study participants will be randomly assigned to open-label study groups, in randomization ratio of 1:1.

In this current multicenter trial, the randomization procedures will be centrally organized. The ratio between treated and control groups should be balanced on each site.

In order to promote balanced allocation within the groups, the study randomization shall be stratified according to APACHE score measured at baseline.

To avoid possible bias in the selection and allocation of subjects and to ensure that the randomization is properly maintained throughout the trial, a computer randomization algorithm will be used for subject allocation to each group. The randomization algorithm will be part of the eCRF. Randomization will be implemented by the PI/Co-investigator after initial screening of the patient is completed (and before starting study procedures).

This will allow first of all the selection of suitable patients, and only then division into groups.

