7.2. Medical condition resulted in the decision to deliver “Comfort-oriented care”

If during the study patient's medical condition changed and the decision/preferences is NOT to receive aggressive, life-sustaining treatments but to delivered comfort-oriented care (or equivalent according to hospital policy and PI confirmation), subject should be terminated from the study.

If in this case the smART+ feeding tube cannot be removed (since a tube must be kept for drainage purposes and a new tube should not be inserted), the feeding tube can continue to be used for drainage / other treatment purposes under the comfort-oriented care.

Although in this case the smART+ feeding tube can be left inside the patient, it must be disconnected from the smART+ device (and all other smART+ components).

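### Section 7.1 classes randomised patients who do not receive the intervention as replaceable screen failures, in conflict with 4.5, 4.6 and 5.1, and section 9 names no analysis set that overrides the label

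*Combined protocol and SAP*

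**What the plan says.** Section 7.1 has two replacement rules. Patients who gave consent and "are randomized but do not receive the study intervention are considered screen failures and may be replaced". Patients who were randomised, received the intervention and "subsequently withdraw, or are withdrawn or discontinued from the study may also be replaced". In both cases replacement is optional and no criteria for using it are given.

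Section 4.5 defines screen failures as people examined at initial screening who "were not subsequently entered to the study". Its examples are ineligibility, missing consent and investigator discretion. The minimum record it asks for covers demographics, the details of the failure, eligibility criteria and serious adverse events. It lists no efficacy outcome.

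Section 4.6 makes inclusion depend on acceptable screening, consent and a pregnancy test where applicable. Section 5.1 has the investigator randomise once initial screening is complete and before study procedures start, and adds: "Study participants will be randomly assigned to open-label study groups".

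Section 7.2 covers patients moved to comfort-oriented care: the "subject should be terminated from the study". Section 7.3 plans no follow-up.

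Section 9.2.2 tests feeding efficiency between the study groups. Nowhere does section 9 name an intention-to-treat, full, per-protocol or safety set.

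**The concern.** The value of a randomised comparison is that the groups differ only by chance at the moment of allocation. Section 7.1 attaches a pre-randomisation label to patients who have already been allocated, and offers to fill their places. Who ends up in this category is decided after allocation is known, and partly by judgement: the investigator may withdraw a patient on health grounds, and replacement is optional.

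Reasons for exit such as failed tube insertion, disease progression or a move to comfort care are plausibly related to prognosis and feeding tolerance. If those patients leave the comparison, if the loss differs between groups, and if those lost differ in outcome, feeding efficiency is no longer compared as randomised. Enrolling a replacement restores the count. It does not restore the patient who was lost.

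**Working it through.** **Step 1. The passages side by side.**

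- 4.5: a screen failure is someone seen at screening and not then entered to the study. Every example it gives comes before randomisation.
- 4.6: inclusion rests on screening, consent and a pregnancy test. Receiving the intervention is not a condition.
- 5.1: suitable patients are selected first and divided into groups afterwards.
- 7.1: a randomised patient can still become a screen failure.

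The documents do not define entry to the study. Reading it as receipt of the intervention would reconcile 4.5 with 7.1, but 4.6 and 5.1 give that reading no support. Section 2.1 does not close the gap either, because it selects the days that count and not the patients. A group A patient fed by a standard tube could still have a feeding-efficiency value from the chart.

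**Step 2. The plan's own figure.** Inputs from 9.1: effect size 0.70, two-sided alpha 0.025, 90% power, 50 per group. The normal approximation gives 51 per group, and power of 0.896 at 50. The noncentral t gives 52 per group, and power of 0.888 at 50. The stated figure reproduces within rounding. Section 9.1 states no allowance for loss.

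**Step 3. Bias on assumed inputs.** The documents give no loss rate and no outcome gap, so both are assumptions. Let a fraction f of one group be lost and replaced by patients like those retained, and let the lost patients be k SD worse than the rest. The retained mean then exceeds the mean of all randomised patients by f × k SD. With no true effect, the test statistic has noncentrality f × k × √(n/2). Alpha 0.025 is carried from 9.1 to both sample sizes; 9.2.1 gives a general 5% level, which would change the baseline.

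With f = 0.10 in group A only:

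| k | Bias (SD) | n per group | Noncentrality | False positives, fixed SD | False positives, simulated |
|---|---|---|---|---|---|
| 0.5 | 0.05 | 50 | 0.05 × 5 = 0.25 | 2.9% | 2.9% |
| 0.5 | 0.05 | 100 | 0.05 × 7.07 = 0.35 | 3.4% | 3.4% |
| 1.0 | 0.10 | 50 | 0.10 × 5 = 0.50 | 4.3% | 4.2% |
| 1.0 | 0.10 | 100 | 0.10 × 7.07 = 0.71 | 6.4% | 6.1% |

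The simulation (200,000 trials per case, pooled t-test) lets the spread widen in the group that keeps the worse patients. Two further cases with k = 1:

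- Equal 10% loss in both groups: the biases cancel, and the rate is 2.5% at either sample size.
- 10% loss in group B only: 4.2% and 6.1%, with the false positives almost all against the device.

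**Step 4. Cost of keeping everyone.** If 10% of group A gain nothing, the effect is 0.70 × 0.90 = 0.63. Power at 50 per group and alpha 0.025 falls from 0.888 to 0.807. At 100 per group it falls from 0.996 to 0.986.

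**The case against.** The strongest reply is that nothing in the documents removes anyone from the analysis. Section 7.1 permits replacement and does not order exclusion. The record in 4.5 is a minimum, so its silence on efficacy does not show that no such data exist. Section 5.1 allocates patients to study groups and 9.2.2 compares study groups, so an as-randomised reading is available. All of this stands. It shows that the matter is unsettled; it does not show that it is settled as randomised. Section 5 describes group A as patients receiving the device, which points the other way.

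A reader might infer that replacement conceals losses. The documents do not support that: 4.5 requires screen-failure details for CONSORT reporting, and 7.1 requires the reason for every discontinuation on the eCRF.

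A reader might also infer that non-receipt falls mainly on group A and so favours the device. That is plausible, since only group A needs the study device placed, but it is not shown. The opening of section 5 says that "The study intervention describes all study procedures and evaluations to be done as part of the study", which covers both groups, so non-receipt can arise in either.

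Nor does 10.1.2 confine data entry to completers. It says when forms must be full. The passage that bears on later data is 7.3. For treated patients who leave early, the days before exit can still give a feeding-efficiency value under 2.1, and nothing says that it is discarded.

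Finally, the illustration depends heavily on the assumed gap: with 0.5 SD in place of 1 SD most of the inflation disappears. For that reason both are shown.

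**Conclusion.** The point holds as a conflict in the text together with a missing definition. Section 7.1 states a rule that 4.5, 4.6 and 5.1 contradict, and section 9 does not override it. Following the rule as written could turn the primary comparison into one among selected patients. That the patients are in fact excluded, or that the trial is biased in a known direction, goes further than the documents allow.

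Actual inflation needs three things that the documents do not establish: exclusion in practice, loss that differs between groups, and a gap in outcome. Under the assumed 10% one-sided loss, a nominal 2.5% error becomes about 3% to 4.2% at 50 per group and 3.4% to 6.1% at 100, for gaps of 0.5 to 1 SD. These are examples and not bounds. The correction does not depend on them, because the population for the primary test should be fixed in advance whatever the loss rate.

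**What to change.** 1. In 7.1 and 4.5, state that screen failure applies only to patients who were not randomised. Extra patients may be enrolled, but they do not substitute for randomised patients in the analysis.
2. In 9.2, make the primary analysis set all randomised patients in their assigned group, except where consent to use of data is withdrawn. Treated and completer sets become sensitivity analyses. Report exits by group, using the reasons already collected.
3. State that the chart data required by 5.2.8 and 5.3.5 are also entered for randomised patients who do not receive the device or who stop it, where consent remains. Reconcile this with 7.3. Where smART+ records are absent, derive feeding efficiency from the chart.
4. Patients with no eligible feeding day have no ratio under 2.1 and cannot enter the test directly. List them by group with the reason, and specify a sensitivity analysis for their absence. This limits how fully item 2 can be met, and the plan should say so.

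The cost is protocol and SAP wording, a little more chart entry, and some dilution: power at 50 per group falls from about 89% to about 81% if 10% of group A gain nothing. No clinical rule changes.
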